**Mar 04, 2015: amendment 03:**

**Primary reason for amendment: addition of centers to the study to conduct the study in multicenter setting. Collection of two fecal samples is added to the protocol.**

## 1. SUMMARY

**Rationale:** Postoperative ileus and anastomotic leakage are complications associated with short-term morbidity and mortality following colorectal surgery. Based on experimental studies, we hypothesize that enriched enteral nutrition shortly before, during and early after colorectal surgery reduces inflammation by stimulation of the autonomic nervous system and thereby postoperative ileus (POI) and anastomotic leakage.

**Objective:** The main objective is to investigate the effects of perioperative nutrition on postoperative ileus and anastomotic leakage in patients undergoing colorectal surgery.

**Study design:** A prospective randomized double blinded controlled trial

**Study population:** Patients undergoing segmental colon/ rectum resection with a primary anastomosis for colorectal cancer >18 years.

**Intervention:** Perioperative nutrition via a nasojejunal tube.

**Main study parameters:** Main clinical outcome parameters are postoperative ileus and anastomotic leakage. Risk of aspiration pneumonia is closely monitored. Before intubation, gastric volumes are measured and the stomach is emptied. The inflammatory response will be quantified by standard assays including Enzyme Linked Immunosorbent Assay (ELISA) and Polymerase Chain Reaction (PCR). Mediators important in the pathogenesis of POI will also be measured in peritoneal lavage fluid. Clinical parameters are prospectively registered in a database and complications are classified using the Clavien-Dindo classification of surgical complications. Other parameters include intestinal barrier integrity and local inflammation in the intestine (measured by PCR and immunohistochemistry). Long-term outcome parameters such as local recurrence, overall and cancer-specific survival will also be registered.

**Nature and extent of the burden and risks associated with participation, benefit and group relatedness:**

All patients will receive a selfmigrating nasojejunal tube (Flocare Bengmark) one day before surgery. The position of the tube is checked via X-ray the same day. Via a specially designed blinded setup (produced by ECM bv, Gemert) patients in the intervention group receive enriched enteral nutrition in low amounts before, during and directly after surgery until oral intake is started. Patients in the control group do not receive nutrition and get a standard preoperative fast until standard oral intake is commenced.

Blood samples will be collected at several predefined moments in relation to the moment of incision. Furthermore, gastric emptying will be assessed via ultrasound before and following a standard meal at day 2 postoperatively. This intervention may benefit the patient by reducing postoperative complications and enhancement of recovery.

Peritoneal lavage is performed at the start of surgery and at the end of surgery. Also gastric content is measured during surgery. It is expected that these procedures will be no burden for the patient.

## 1. INTRODUCTION AND RATIONALE

Postoperative ileus and anastomotic leakage are important clinical determinants of short-term morbidity and mortality following colorectal surgery. Importantly, anastomotic leakage is also a risk factor for local recurrence of colorectal cancer and has a significant impact on disease-free and overall survival. It is therefore believed that improving postoperative outcome following colorectal surgery will also improve long-term oncological outcomes regarding overall survival and tumour recurrence.

Postoperative ileus (POI) is a common complication after colorectal surgery that causes discomfort for the patient but also leads to a prolonged hospital length of stay and increasing health care costs. Although the underlying mechanism has been studied extensively in animal experiments, targeted therapeutical strategies are lacking in a clinical setting and only supportive arrangements are taken to optimize the patient's condition. For POI it is believed that formation of an inflammatory infiltrate in the muscular layers of the intestine following bowel manipulation during surgery leads to a decreased gastrointestinal motility. In recent years our group has demonstrated in experimental models that administration of enteral nutrition modulates the inflammatory response via the autonomic nervous system by release of cholecystinin (CCK). Composition of the enteral nutrition and timing of administration are both essential for the magnitude of effect. For the most optimal effect, nutrition is given with a higher fraction of lipids and protein and is administered just before, during and directly after the inciting event. In this way, the inflammatory response is optimally dampened via release of CCK. In an experimental study has been shown that such a lipid-enriched enteral nutrition reduces systemic inflammation and postoperative ileus in a CCK-dependent manner when given just before and directly after bowel manipulation.

Next, we performed a study in healthy volunteers in which the effect of continuous low volume enteral nutrition was investigated on inflammatory parameters in a human endotoxemia model. In this study was shown that lipid enriched nutrition reduced the inflammatory response upon endotoxemia in man.

Also in a clinical setting we have shown that enteral nutrition reduces inflammation and POI. In a randomized controlled trial our group has shown that enteral nutrition early after colorectal surgery reduced POI. Furthermore, in a model of sham-feeding using chewing gum was shown that inflammation and POI were reduced following colorectal surgery (vd Heijkant et al, accepted in The British Journal of Surgery).

Interestingly, both clinical studies with sham feeding and early enteral nutrition revealed a yet unaccountable effect on anastomotic leakage. Evidence on the relation between POI and anastomotic leakage is scarce but has great impact. Early inhibition of the inflammatory response may play a role since release of proinflammatory cytokines such as TNF- $\alpha$  modulates intestinal epithelial function and is an inhibitory factor in the wound healing process of intestinal anastomoses. Therefore, it seems that an early intervention with enteral nutrition shortly before, during and early after colorectal surgery may reduce inflammation and reduce important determinants in postoperative morbidity as POI and anastomotic leakage. In the current study we plan to investigate the effectiveness of perioperative nutrition compared with standard of care (nil-per-mouth) in a large-scale trial in patients undergoing colorectal surgery.

## **2. OBJECTIVE**

### **2.1 Primary objective**

To investigate the effect of perioperative nutrition on postoperative ileus and anastomotic leakage in patients undergoing colorectal surgery with primary anastomosis compared with standard care.

### **2.2 Secondary objectives**

To investigate the effect of preoperative nutrition in colorectal surgery on:

- Aspiration pneumonia
- Gastric volumes preoperatively
- Length of functional recovery
- The pro- and anti-inflammatory response both locally, systemically and in peritoneal lavage fluid
- Damage to the intestinal barrier (I-FABP)
- Need for additional surgical, radiological or endoscopic interventions
- Other complications requiring treatment (i.e. urinary tract infection)
- Need for ICU admission and total length of ICU stay
- Cost-effectiveness ratios

## **3. STUDY DESIGN**

A prospective randomized double blinded controlled trial performed at the Catharina Hospital Eindhoven. **We start the trial in one centre, and continue the trial in multicentre setting. Participating centres can be found in Appendix B.** It is expected that patients will be included over a period of 3 years. At our hospital it was shown in previous studies that at least 75-100

patients undergoing colorectal surgery each year can be included. Most included patients will have colorectal cancer. Due to the nationwide screening program for colon cancer, it is expected that the amount of colorectal operations will further increase. In the experimental group patients receive enriched enteral nutrition. In the control group patients receive standard of care (enhanced recovery after surgery protocol).

## **4. STUDY POPULATION**

### **4.1 population (base)**

Patients undergoing segmental colon resection with primary anastomosis.

### **4.2 inclusion criteria**

- patients that undergo elective surgical resection with primary anastomosis.
- written informed consent
- age >18 years

### **4.3 exclusion criteria**

- use of medication that disrupts acetylcholine metabolism
- steroid use
- previous gastric or oesophageal resection
- peritoneal metastases found during surgery
- pre-existent or creation of an ileostomy

### **4.4 Definitions**

Anastomotic leakage is defined as clinical and radiological signs of anastomotic leakage, or confirmed by re-operation or occurrence of an enterocutaneous fistula. Postoperative ileus will be assessed as time to first flatus and defaecation and by measurements of gastrointestinal transit times via ultrasonography (using antrum measurements). Aspiration pneumonia is defined as inflammation in the lungs following aspiration of material (solid or liquid, vomit, saliva).

### **4.5 Sample size calculation**

Patients will be recruited at the outpatient clinic of the Catharina Hospital Eindhoven. Reduction of anastomotic leakage and postoperative ileus are primary outcome parameters for the sample size calculation. Anastomotic leakage is the most detrimental complication

following colorectal surgery associated with high hospital costs and also with effects on long-term general and cancer-specific outcome. We have performed two clinical studies in colorectal surgery patients that can be used as basis for the power calculation. In one study in which we compared very early enteral nutrition with very early parenteral nutrition, we observed a reduction of anastomotic leakage from 12.9% in the parenteral group to 1.6% in the enteral group. However, this effect may be confounded by the potential detrimental effect of parenteral nutrition. Early postoperative ileus reduced in this study from 35% in the parenteral group to 16% in the enterally fed patients.

In a second study, the effect of sham-feeding via chewing gum on postoperative ileus was compared with controls. In this study postoperative ileus was reduced from 47% in the controls to 27% in the intervention group. The effect on anastomotic leakage was also apparent and leak-rates reduced from 13% in the placebo group to 3% in the intervention group

Based on these previous results a power calculation can be performed. For postoperative ileus a sample size of at least 91 patients per group is needed based on a power of 0.8 and an alpha of 0.05. For anastomotic leakage a reduction of anastomotic leakage of at least 75% was observed in the previous clinical studies. Using a power of 0.8 and a drop-out percentage of 5% a total of 140 patients are needed per group. Since perioperative nutrition is a new concept, an interim analysis is performed after inclusion of 40 patients in which feasibility and safety of preoperative nutrition are assessed. All analyses will be done according to the intention-to-treat approach in which all randomised patients are included, regardless of adherence to study protocol. Occurrences of the primary and secondary endpoints are compared between the treatment groups. Results are presented as risk ratios with corresponding 95% confidence intervals. A two-tailed  $P < 0.05$  is considered statistically significant.

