## 6. METHODS

### 6.1 Primary endpoint

- Postoperative ileus

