### 6.2 Secondary endpoints

- Anastomotic leakage
- Aspiration pneumonia
- Gastric volumes preoperatively
- Length of functional recovery
- The local and systemic inflammatory response
- Surgical complications
- Length of stay
- Intestinal barrier function and local inflammation in the gut
- Need for additional surgical, radiological or endoscopic interventions
- Need for ICU admission and total length of ICU stay
- Quality of life (EQ-5D-5L and EORTC-QLQ-C30 at baseline, after 3 and 6 months)
- Cost-effectiveness ratios (iMCQ and iPCQ at baseline, after 3 and 6 months)
- Composition of faecal microbiome

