### **8.6 Premature termination of the study**

In addition to safeguarding the safety of the patients in the study, the DSMB will check for early proof of efficacy during an interim-analysis for benefit which will be performed halfway the study. If the DSMB suspects harm there will be a meeting between the DSMB, the study group and an independent statistician. During this meeting there should be a discussion about any potential causal relation between early start of postoperative oral nutrition and harm.

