## **9. STATISTICAL ANALYSIS**

All analyses will be done according to the intention-to-treat approach in which all randomized patients are included, regardless of adherence to study protocol. Occurrences of the primary and secondary endpoints are compared between the treatment groups. Results are presented as risk ratios with corresponding 95% confidence intervals. A two-tailed  $P < 0.05$  is considered statistically significant. To compare the groups the data will be tested for normal distribution and an unpaired T-test will be performed when appropriate, otherwise the Mann-Whitney U or Chi-square tests.

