## 12. STRUCTURED RISK ANALYSIS

### 12.1 Potential issues of concern

The enriched enteral nutrition that is used, has been investigated before in healthy volunteers during endotoxemia. In this study there were no adverse or serious adverse events. Enclosed is the diet composition.

a. Level of knowledge about mechanism of action: The mechanism has been extensively shown in experimental models. A (pre) clinical study in healthy volunteers and a prospective randomized controlled trial in patients undergoing colorectal surgery showed results in line with the found hypothesis.

b. Previous exposure of human beings with the test product(s) and/or products with a similar biological mechanism. As mentioned before, the enteral nutrition that is used, has been investigated before in healthy volunteers during endotoxemia.

c. Can the primary or secondary mechanism be induced in animals and/or in *ex-vivo* human cell material? Yes

d. Selectivity of the mechanism to target tissue in animals and/or human beings. The found effects in previous studies is specifically targeting the inflammatory response and has shown to affect both anastomotic leakage and postoperative ileus, the two primary outcome parameters.

e. Analysis of potential effect. The nutrition itself is not considered to be harmful. Administration of enteral nutrition during surgery is a new concept. For this reason a data safety monitoring board is installed. There have been no described effects at all. A potential complication is aspiration pneumonia.

f. Pharmacokinetic considerations: *not applicable*

g. Study population. Patients undergoing colorectal surgery with primary anastomosis.

h. Interaction with other products: *not applicable*

i. Predictability of effect. The found effects in animal experiments were on both the inflammatory response and clinical parameters. The effects were consistent in various experimental models and in the clinical studies.

j. Can effects be managed? During surgery, gastric volumes are measured and gastric content is aspirated to minimize risk of aspiration pneumonia.

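### The plan gives two answers on whether anastomotic leakage is a primary endpoint, and no rule for reading a result that is significant on leakage alone

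*Combined protocol and SAP*

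**What the plan says.** Section 6.1 lists one primary endpoint, "Postoperative ileus". Section 6.2 opens its list of secondary endpoints with "Anastomotic leakage".

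Other current sections treat the two as a pair:
- The Summary names both as the main clinical outcomes.
- Section 2.1, the primary objective: "To investigate the effect of perioperative nutrition on postoperative ileus and anastomotic leakage in patients undergoing colorectal surgery".
- Section 4.5: "Reduction of anastomotic leakage and postoperative ileus are primary outcome parameters for the sample size calculation".
- Section 12.1, item d: "both anastomotic leakage and postoperative ileus, the two primary outcome parameters".

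Section 4.5 asks for at least 91 patients per group for POI. For leakage it says: "Using a power of 0.8 and a drop-out percentage of 5% a total of 140 patients are needed per group".

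On testing, section 9 says "Occurrences of the primary and secondary endpoints are compared between the treatment groups", and sections 4.5 and 9 both set significance at two-tailed P<0.05. Neither gives a test order, an alpha split or a requirement that both endpoints succeed. Section 8.6 adds that "the DSMB will check for early proof of efficacy during an interim-analysis for benefit which will be performed halfway the study", without naming the endpoint. Appendix II makes the DSMB responsible for stopping guidelines before its first data review, but it does not say which endpoint is primary.

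**The concern.** The primary endpoint decides whether a confirmatory trial has succeeded. Here one result is read in opposite ways depending on the section. If leakage is significant and POI is not, section 6.1 gives a failed primary with a supportive secondary finding, while section 12.1 would let the same data be presented as success on one of two primaries.

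Leakage is not a minor item in the list. It gives the larger sample size, and section 4.5 calls it the most detrimental complication after colorectal surgery. The pull towards claiming it would be strong. With no written rule, the choice could be made after the data are seen, and a choice made then could not be defended.

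**Working it through.** **1. The sections side by side**

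| Place | POI | Leakage |
|---|---|---|
| 6.1 / 6.2 | primary | secondary |
| 12.1 item d | primary | primary |
| 4.5 | primary, for sample size | primary, for sample size |
| 2.1 | in primary objective | in primary objective |
| Summary | main outcome | main outcome |

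Only 12.1 contradicts section 6 outright. The other three lean the same way as 12.1.

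**2. The plan's sample sizes**

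Inputs from section 4.5: power 0.80; alpha 0.05, stated for POI and assumed two-sided for leakage; 5% drop-out for leakage; and the chewing-gum study's rates, POI 47% vs 27% and leakage 13% vs 3%. The leakage rates behind 140 are not stated (only a reduction of at least 75%), so 13% vs 3% is inferred.

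Formula per group, with p̄ the mean of the two rates: n = [1.960·√(2p̄(1−p̄)) + 0.8416·√(p₁(1−p₁)+p₂(1−p₂))]² / (p₁−p₂)².

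- POI: (1.338 + 0.562)² / 0.04 = 90.3, so **91**. This matches.
- Leakage: (0.752 + 0.317)² / 0.01 = 114.3, so 115 uncorrected. The continuity correction, n/4·[1+√(1+4/(n·0.10))]², gives 133.6, so 134. Drop-out gives 134/0.95 = 141.1 or 134×1.05 = 140.7, that is **141–142**, against 140 stated.

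So leakage gives the larger figure. An assumed 12% vs 3% without correction also fits (134, then 142).

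**3. Chance of a leakage-only result**

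Evaluable per group: 140 × 0.95 = 133. Power is by exact binomial enumeration of the chi-square test at two-sided 0.05, with POI as yes/no.

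| | Uncorrected | Continuity-corrected |
|---|---|---|
| POI, 47% vs 27% | 0.927 | 0.907 |
| Leakage, 13% vs 3% | 0.884 | 0.827 |
| Leakage only = (1 − POI power) × leakage power | 0.065 | 0.077 |

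The product assumes independent endpoints. With an assumed patient-level correlation of 0.2, simulation gives 5.9% / 6.8%. At the enteral-versus-parenteral study's rates (POI 35% vs 16%, leakage 12.9% vs 1.6%) the chance is 4.7% / 6.3%. As a sensitivity case on my own assumption, halving the POI effect (47% vs 37%) and keeping the full leakage effect gives about 54%.

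**4. Type I error under each reading**

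- POI alone governs: nominal 5%.
- Both required: no excess over 5%.
- Either suffices: 1 − 0.95² = 9.75% under independence, and about 9.1% at an assumed correlation of 0.5 between the test statistics.

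**5. Power under each possible rule** (133 evaluable; uncorrected / corrected)

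- Leakage tested only after POI succeeds: 0.927 × 0.884 = 0.82; 0.907 × 0.827 = 0.75. Requiring both gives the same figures.
- 0.025 each: leakage 0.81 / 0.74; POI 0.88 / 0.85.
- Sample size for leakage at 0.025 (2.241 replacing 1.960): 138.6, so 139 evaluable uncorrected (139/0.95 = 146.3 per group); 158 evaluable corrected (158/0.95 = 166.3, so 167 per group).

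**The case against.** The strongest reply is that section 6 is where endpoints are defined, and it is clear. Section 4.5 speaks only of the sample size, and sizing a trial on a rarer, important secondary endpoint is legitimate. Section 2.1 is an objective, not a success rule. Section 12.1 is a passing phrase in a risk-analysis item about mechanism, and it sets no test. On this view a leakage-only result is, by convention, a failed primary.

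Much of this stands. It shows that the conflict can be settled by wording, and that 6.1/6.2 is the natural reading to settle on. It does not show that the plan has settled it: no section says that section 6 prevails, and neither 2.1 nor 12.1 carries the qualifier found in 4.5.

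A reader might infer more than the documents support:
- That the trial runs at 9.75% type I error. No section says that either endpoint suffices; the figure belongs to one unstated reading.
- That a leakage-only result is likely. The 54% case pairs a full leakage effect with half the POI effect, whereas both earlier studies in section 4.5 saw the two outcomes fall together. It should not drive severity.
- That the sample size is wrong. Both figures reproduce, although at the chewing-gum study's rates they need different formulas.

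**Conclusion.** The contradiction is real and stands in current text. The plan does not fix how a result significant on leakage alone is to be read. At the chewing-gum study's rates that result has about a 6–8% chance, and the chance is larger if the POI effect is smaller than assumed. This rests on 13% vs 3% being the basis of 140, on 133 evaluable patients per group, on independent endpoints, and on POI as a yes/no outcome. Section 4.4 does not fix the last of these; it assesses POI by times to flatus and defaecation and by ultrasound.

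Error inflation is conditional. It is at most a nominal 9.75% under independence if either endpoint were allowed to suffice, and there is none from this source if 6.1 governs or both are required.

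Should-fix: the success criterion is inconsistent, but wording resolves it without more patients.

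**What to change.** Before unblinding and before the halfway efficacy look, conform the Summary and sections 2.1, 4.5, 9 and 12.1 to 6.1/6.2. Suggested text:

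> POI is the single primary endpoint, tested at two-sided 0.05. Anastomotic leakage is the key secondary endpoint, tested confirmatorily at two-sided 0.05 only if POI is significant; otherwise it is reported as supportive.

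In 4.5, state that leakage sets the 140 per group. Any POI power quoted there (about 91–93% for 47% vs 27% at 133 evaluable per group) must say that it assumes a yes/no POI endpoint. In 8.6, name POI as the endpoint of the efficacy look, so that the DSMB's guidelines refer to it.

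**Cost.** The sample size does not change. Leakage cannot be claimed confirmatorily if POI fails, so power for that claim falls from about 0.88 to 0.82 uncorrected, or from 0.83 to 0.75 continuity-corrected.

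**If the sponsor keeps both as primary**, it must state either that both are required or how alpha is split, and restate power at 140 per group. At 0.025 each, exact leakage power is about 0.81 uncorrected or 0.74 corrected. The continuity-corrected formula that reproduces 140 would call for about 167 per group, so 80% power should not be claimed by that method. Even the uncorrected formula gives about 146.
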